There is increasing published evidence that some fluids may leave the stomach earlier than expected – well within the two-hour window traditionally advised. If fluid has left the stomach it cannot be regurgitated. Different fluids may leave the stomach at different times, however, there have been no recent studies that examine how quickly water leaves the stomach.

Our study will assess how quickly water leaves the stomachs of healthy volunteers. We will give participants water and scan their stomachs with ultrasound to see how long it takes for the water to exit. If water exits the stomach rapidly, and in a shorter time frame than the two-hour window currently used, we may eventually be able to allow patients to drink water closer to the time of their operation, reducing their discomfort and increasing satisfaction without any increased risk of aspiration.

Background

Current national and international guidelines require that patients are subjected to a fasting period of six hours for solids and two hours for clear fluids prior to surgery under general anaesthesia to minimise the risk of aspiration of gastric contents.¹ In addition to the adverse effects of fasting on patient comfort, the development of 'enhanced recovery pathways' for surgery has raised awareness of the importance of optimal perioperative fluid balance and haemodynamic status.² Whilst it is difficult to link different fasting regimens to clinical outcomes, there is general agreement that it is beneficial to minimise fasting times where possible. Surgical intervention exposes patients to significant physiological stress and with the current guidelines most patients are subjected to dehydration and hunger at some stage preoperatively. Furthermore, if the conventional two hour fasting guideline for clear fluids can be safely reduced this could contribute to increased patient comfort and reduced feelings of thirst. It is estimated that over 2.7 million patients received a general anaesthetic in the UK in 2013,³ thus the implications of fasting affect a large part of the population.

The volume of fluid in the stomach – the gastric volume, a surrogate marker for risk of aspiration – can be measured rapidly and non-invasively using ultrasound imaging with widely available equipment. Studies have shown that estimated volumes using ultrasound correlate well with assessment by other modalities, with a recent review supporting the use of cross-sectional area measurement with ultrasound in determining gastric volume.^{4,5}

Recently there has been interest in challenging conventional fasting times, particularly for nonclear fluids (milky drinks and carbohydrate drinks).^{6,7} However, to date there have been no studies involving administering water alone and assessment with ultrasound.

Aims

- Primary aim: To establish if it is possible to use ultrasound to collect data on gastric volume in volunteers following 2 study protocols called 'Protocol NBM' and 'Protocol H₂O'.
- To determine if volunteers can be recruited, how long the protocols last and whether there are any unknowns that require answering prior to designing a full trial.
- To use the primary outcomes in each protocol and their standard deviations to estimate the sample size required for a full trial.

Trial Design

This is a feasibility study, with features that may assist in the design of a pilot/full study. The volunteers will abstain from eating and drinking calorie containing beverages for 4 hours, and then be randomised to being nil by mouth 'Protocol NBM' or to have 2x150ml drinks of water 'Protocol H₂0'. The trained researcher performing the ultrasound measurement of gastric volume will be blinded as to which intervention has occurred. On a subsequent session >1 week later, the volunteer will repeat the fast and follow the alternative intervention e.g. randomised crossover interventional study. Participants in this feasibility study will act as their own controls by undertaking both protocols. This study is preliminary work to establish proof of concept. The future objective, after subsequent ethics applications, will be to repeat the study in patients undergoing operations under local anaesthesia and then general anaesthesia

Figure 1: Protocol Overview

Outcome Measure

The primary outcome is the gastric volume measured at specific intervals following protocols of either nil by mouth 'Protocol NBM' or having 2x150ml drinks of water 'Protocol H₂0', and the standard deviation of that measure. The ability of a full trial to establish a difference in primary outcome between 'Protocol NBM' and 'Protocol H₂0' is dependent on the size of any difference measured, and the standard deviation.

Recruitment and Sample Size

Fifteen healthy volunteers will be recruited in a variety of ways including, but not limited to, poster advertisement in the Musculoskeletal Research Unit. At this stage of recruitment, participants will be informed that gastric emptying will be measured during the study, and that ultrasound will be used to obtain the measurement.

Inclusion Criteria

- Adult (aged over 18 years)
- Ability to attend on two separate days to complete both protocols 'day A' and 'day B'.

Exclusion Criteria

- Participants must not be pregnant, not be trying to get pregnant and not think they may be pregnant
- Participants must not be taking medication that may influence appetite and/or digestion of food (except oral contraceptive pills).
- Participants must not have a history of any medical condition that may affect appetite and/or digestion of food e.g. previous gastro-duodenal surgery, diabetes mellitus, advanced liver or renal disease, recent gastrointestinal infection (within one month).
- Conditions that affect ability to obtain accurate data with ultrasound e.g. obesity (BMI>35), previous gastro-duodenal surgery

Attendance

On day A participants will be randomised via computer software to either undertake 'Protocol NMB' (conventional fasting) or 'Protocol H_2O' (drinking water). On day B (which should be at least a week later) the participant will undertake the other protocol not yet completed. Where possible the participants will complete the two protocols at approximately the same time on each day (morning or afternoon). The two attendance days A and B will be separated by at least 1 week and no more than 2 months.

Consent

Before participants take part in the study, it is important to ensure they are adequately informed about the procedures used in the study, the mandatory participation criteria and the level of staff training on 2D ultrasound.

Participants will be emailed an information sheet to read prior to taking part in the study informing them that ultrasound will be used to measure gastric emptying during the study and i) what ultrasound is ii) what to expect from the scan iii) what risks are associated with ultrasound.

Upon arrival at the test sessions, participants will be given this information sheet to read again. In addition, they will read the document 'Risks associated with the use of ultrasound' (Appendix A)

Participants will be given the opportunity to ask any questions they may have. Questions will be answered by the researcher.

Before the participants complete the consent form they must be informed that the ultrasound scan is for research purposes only and is not a diagnostic scan and must be made aware of the 'Incidental findings policy' (Appendix B)

Participants will be given two consent forms to complete – one for the researcher and one for the participant to keep. A copy of the consent form will be kept in a site file.

Intervention

Preparation

- Screening questionnaire participants identified who meet inclusion and exclusion criteria
- Study information and consent process

- Dates and times given for study attendance
- Fasting instructions and times given
- A record of the content and timing of the light breakfast prior to the period of fasting, and amount, type and timing of clear fluids self-administered during the subsequent 4 hour period of free clear fluids, will be kept by the participant
- No alcohol and no major exercise other than 'usual activities' for 24 hours prior to attendance to reduce the risk of dehydration

Intervention

- Abstinence from eating and drinking calorie containing beverages for 4 hours then either oral water administration or nil by mouth for 2 hours, during which ultrasound measurements of gastric volume are made. (see Figure 1 'Protocol Overview' above):
 - 'Protocol NBM': light breakfast followed by a period of four hours during which the volunteer abstains from eating and drinking calorie containing beverages, followed by a further 2 hours of complete fast (i.e. nil by mouth) during which ultrasound measurements of gastric volume are made.
 - 'Protocol H₂O': light breakfast, followed by a period of four hours during which the volunteer abstains from eating and drinking calorie containing beverages, followed by two 150ml drinks of water an hour apart, during which ultrasound measurements of gastric volume are made. Ultrasound measurement of gastric volume may optionally continue for a further two hours if return to the starting gastric volume is not achieved.
- Sonographers will be blinded as to which protocol the participant has been allocated. Blinding of participants will not be possible.
- Ultrasound scans will take place prior to any water administration, then at 30
 minute intervals, with gastric volume ascertained using the techniques described in
 references 4 and 5.
- If the baseline gastric volume measured at the beginning of the protocol has not been achieved following two hours then further scans will occur at 30 minute intervals until either the starting gastric volume is achieved or a further two hours

• Participants will be asked to rate their comfort, thirst, hunger and anxiety levels every hour (numerical scale 1 to 10)

Adverse Events

An Adverse Event (AE) is defined as any untoward medical occurrence in a volunteer, not necessarily having a causal relationship.

A Serious Adverse Event (SAE) is defined as any untoward and unexpected medical occurrence or effect that:

- Results in death
- Is life-threatening refers to an event in which the subject was at risk of death at the time of the event; it does not refer to an event which hypothetically might have caused death if it were more severe
- Requires hospitalisation
- Results in persistent or significant disability or incapacity
- Is otherwise considered medically significant by the investigator

Medical judgment will be exercised in deciding whether an AE is serious. Important AEs that are not immediately life-threatening or do not result in death or hospitalisation but may jeopardise the subject or may require intervention to prevent one of the other outcomes listed in the definition above, will also be considered serious.

It is considered very unlikely that any such event would occur during the course of this healthy volunteer study with a non-invasive investigation.

Unrelated Adverse Events

Adverse events unrelated to the trial procedures are:

None known

Expected Adverse Events

Possible (expected) adverse events related to the trial procedures are:

• In the event that an ultrasound scan reveals a suspected abnormality that was unknown to the Study Research Team and which they suspect might require

treatment, the 'Incidental findings policy' (Appendix B) will be followed.

Reporting Procedures

The Chief Investigator (CI), will notify the study sponsor (University of Bristol) within 72 hours of receiving the SAE and report any related and unexpected SAEs to the main Research Ethics Committee within 15 days of the CI becoming aware of the event.

Contact details for reporting SAEs:

[name] Email: [contact]

Statistical Analysis

This is a feasibility study designed to establish whether a complete set of data can be collected following each of the protocols. The primary outcomes in each protocol and their standard deviations will be used to estimate a sample size requirement for a future full trial. 15 cases should provide reasonable precision for this calculation.

Data Storage

All the information collected will be kept strictly confidential and will be used only for the purposes of this project. All names will be removed from the information provided by participants. No names or details that might allow identification of individuals will be reported in any research papers, or to anyone outside the research team. Local data will be temporarily stored with a unique ID on a password-protected computer. All data will then be stored on the University of Bristol secure server accessed through the remote desktop from outside the University.

Sponsorship and Insurance

The University of Bristol will provide sponsorship and insurance for the study.

Funding

This project has been awarded a grant of £19775 from the David Telling Charitable Trust, Bristol, UK.

Gantt chart of approximate timeline:

	Week 1	Week 2	Week 3	Week 4	Week 5	Week 6	Week 7	Week 8	Week 9	Week 10	Week 11	Week 12	Week 13	Week 14	Week 15	Week 16
Volunteer:																
1	Day A	Day B														
2	Day A	Day B														
3	Day A	Day B														
4	Day A	Day B														
5					Day A	Day B										
6					Day A	Day B										
7					Day A	Day B										
8					Day A	Day B										
9									Day A	Day B						
10									Day A	Day B						
11									Day A	Day B						
12									Day A	Day B						
13													Day A	Day B		
14													Day A	Day B		
15													Day A	Day B		

References

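### Sonographer blinding is stated but not protected, and the serial scans and the two-hour return-to-baseline check can plausibly break it

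*Protocol*

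**What the plan says.** The protocol asserts assessor blinding twice. Trial Design states "The trained researcher performing the ultrasound measurement of gastric volume will be blinded as to which intervention has occurred". The Intervention section states "Sonographers will be blinded as to which protocol the participant has been allocated. Blinding of participants will not be possible".

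The procedures around that claim are these:

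- **Scan schedule (Intervention):** "Ultrasound scans will take place prior to any water administration, then at 30"-minute intervals.
- **Water load (Intervention, Protocol H2O):** "followed by two 150ml drinks of water an hour apart". Protocol NBM takes nothing over the same two hours.
- **Extension (Intervention):** one bullet, not limited to either protocol, says "If the baseline gastric volume measured at the beginning of the protocol has not been achieved following two hours then further scans will occur" every 30 minutes, for up to two more hours. The Protocol H2O description also contains an extension, but there it is optional and the Protocol NBM description has no counterpart.
- **Crossover (Attendance):** "On day B (which should be at least a week later) the participant will undertake the other protocol not yet completed".

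Outcome Measure makes gastric volume at these time points, with its standard deviation, the primary outcome. Aims and Statistical Analysis use both to size a full trial.

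**The concern.** The measured quantity is itself the sign of allocation. One protocol puts 300 ml into the stomach after baseline and the other puts in nothing, and the person called blinded is looking at the stomach. Withholding the allocation from that person does not keep it from them.

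The text gives no safeguard. It does not say who gives the water, whether participants (who know their protocol) must keep silent, whether images are stored and read later under a mask, or whether a different sonographer attends on day B.

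A reader who knows the protocol, the time point and the earlier values can drift towards the expected pattern: flat under NBM, up and back to baseline under H2O. That could shift the paired difference and make serial readings look more consistent than they are. Both feed the sample size of the full trial, which might also take over the method under the label of a blinded assessment.

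**Working it through.** The protocol gives no figure on blinding, so there is nothing to reproduce. The check has three parts.

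**1. Which readings are exposed**

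Inputs from the protocol: 15 volunteers, 2 sessions each, scans at baseline and every 30 minutes for two hours (taken as 0, 30, 60, 90 and 120 min), with possible extension to 240 min (4 more scans).

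- Post-baseline scans in the first two hours: 15 x 2 x 4 = 120.
- Extension scans: at most 15 x 2 x 4 = 120 if both protocols can be extended, or 15 x 1 x 4 = 60 if only Protocol H2O can.
- Day-A baselines (15): these precede any water, so no scan can yet have given a clue. Not at risk by this route.
- Day-B baselines (15): at risk only if a day-A guess carries over.
- All scans, for costing: 15 x 2 x 5 = 150 without extension; 15 x 2 x 9 = 270 if every session is extended; 15 x 9 + 15 x 5 = 210 if every H2O session and no NBM session is.

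**2. How far the readings could reveal the protocol**

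This part rests on assumptions that are not in the protocol. Each 150 ml drink (at 0 and 60 min, the second after the 60-min scan) leaves 150 x 2^(-t/h) ml after t minutes, for half-time h of 5 to 30 min. True NBM volume is stable. Readings carry independent error with SD 10 to 40 ml.

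*Any rise.* With five exchangeable readings, baseline is the highest with probability 1/5. At least one later scan therefore exceeds baseline in 1 - 1/5 = 80% of NBM sessions by reading error alone. Simulated H2O sessions give 81% to about 100%. A rise of any size is weak evidence.

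*The pattern of rises.* Let d be the four expected changes from baseline under H2O and C = SD² x (I + J) their covariance, with I the identity and J a matrix of ones. With D = sqrt(d' C⁻¹ d), best-guess accuracy is Φ(D/2) for one session and Φ(D√2/2) for both days combined. Chance is 50%. At SD 20 ml:

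| Half-time (min) | Water left at 30 min (ml) | One session | Both days |
|---|---|---|---|
| 5 | 2 | 53% | 54% |
| 10 | 19 | 68% | 75% |
| 15 | 38 | 82% | 90% |
| 20 | 53 | 90% | 96% |
| 30 | 75 | 96% | 99.5% |

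As a check, at h = 20, d = (53.0, 18.8, 59.7, 21.1). Then D² = (7,172 - 152.6²/5)/400 = 6.29, D = 2.51, and Φ(1.25) is about 0.90. Over all assumed values, one-session accuracy runs from 51% (h = 5, SD 40 ml) to about 100% (h = 30, SD 10 ml). The last column needs the same sonographer on both days.

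**3. What the extension rule requires**

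The trigger is "If the baseline gastric volume measured at the beginning of the protocol has not been achieved following two hours". To apply it, someone must work out the two-hour volume and compare it with that session's baseline before the participant leaves, so not every reading can be deferred. If the extension belongs to Protocol H2O only, as its arm description can be read, an extended session shows the arm directly. If the general bullet governs, it does not.

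**The case against.** The strongest reply is that nothing in the text discloses the allocation to the sonographer. The blinding statements are not false as written, and an outcome that hints at treatment is common to interventions that work. Figure 1 was not available to me, and site procedures may cover handling. This is a 15-person feasibility study with no hypothesis test. Much of this stands: it makes unmasking a risk rather than a demonstrated failure, and it limits the consequences.

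A reader might go further than the protocol supports in four ways:

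- **That any rise after baseline identifies Protocol H2O.** It does not: reading error alone would give such a rise in about 80% of NBM sessions, and very fast emptying could leave little to see at 30 minutes. Only a clear rise is informative.
- **That one person reads every scan live, on both days.** The protocol speaks of one trained researcher in one place and of sonographers in another. It does not say who calculates volumes or makes the two-hour comparison. Carry-over between days is conditional on this.
- **That every reading is compromised.** Day-A baselines are not.
- **That the bias has a known size in millilitres.** The protocol offers no basis for one.

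The reply does not answer the central point. Blinding is presented as a feature of the design, the procedures work against it, and no safeguard is described. Nor can it wait for an analysis plan, because images that were not stored cannot be re-read under a mask.

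**Conclusion.** The point holds as a weakness in how the primary outcome is measured: blinding is asserted, unprotected and plausibly breakable. At risk are 120 post-baseline readings, up to 60 or 120 extension readings depending on which extension rule governs, and 15 day-B baselines if the same sonographer, or shared knowledge, links the two days. The chance of a correct guess depends on emptying rate and reading error, neither of which the protocol gives; under the assumed ranges it runs from near chance to near certainty. The size and direction of any resulting bias in the volumes or their SDs cannot be derived.

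A reader might infer that the assessment is in fact unblinded. The protocol does not establish that. What it supports is a cheap change to the measurement method, worth making before the first scan because these volumes and SDs are what the full trial will be sized on.

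**What to change.** 1. Store the images from each scan under a random code, with participant ID, day and time masked.
2. Have the existing sonographer(s) measure them once both sessions are complete, in random order across participants, days and time points. Use these readings as the primary-outcome data.
3. Use live readings only for the two-hour return-to-baseline check.
4. Reconcile the two statements of the extension: optional and under Protocol H2O, or a general rule for both protocols.
5. If masked reading is not adopted, describe the assessor as not told the allocation rather than as blinded.

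**Cost.** Image storage and reading time from existing staff: 150 x 2 min = 5 hours, up to 270 x 2 min = 9 hours, at an assumed 2 minutes per scan. Volumes become available later.

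**Limits.** The protection is partial. Images are still acquired by an operator who may be unmasked, and a fluid-filled stomach stays recognisable, although it can no longer be tied to a participant, day or baseline value.

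### Scanning after two hours is governed by two conflicting rules, and the one stated only for Protocol H2O would unblind the late scans and leave them without controls

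*Protocol*

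**What the plan says.** All the relevant text is in the Protocol; the scanning rules are under Intervention.

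- **Protocol NBM** is four hours without food or caloric drinks, "followed by a further 2 hours of complete fast (i.e. nil by mouth) during which ultrasound measurements of gastric volume are made". No extension is mentioned.
- **Protocol H2O** has the same four hours, then two 150 ml drinks an hour apart. Its description adds: "Ultrasound measurement of gastric volume may optionally continue for a further two hours if return to the starting gastric volume is not achieved".
- **A later bullet** stands at the same level as the blinding and scan-schedule bullets, which cover both protocols. It reads: "If the baseline gastric volume measured at the beginning of the protocol has not been achieved following two hours then further scans will occur", every 30 minutes until baseline is regained or two more hours have passed.
- **Blinding:** "Sonographers will be blinded as to which protocol the participant has been allocated". Trial Design also says the person scanning is blinded to the intervention.
- **Design and outcome:** Trial Design says "Participants in this feasibility study will act as their own controls by undertaking both protocols". Under Outcome Measure, "The primary outcome is the gastric volume measured at specific intervals following protocols of either nil by mouth" or the water protocol, together with its standard deviation. Statistical Analysis uses the outcomes and their SDs to size a future trial.

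No text at hand says which continuation rule governs. Figure 1, the protocol overview, is not shown and might bear on it.

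**The concern.** Staff running a session that has not returned to baseline at two hours are told two different things. The rule governs conduct on the day, so a statistical analysis plan written later could not repair it.

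Three things are at stake.

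1. **Blinding.** If only H2O sessions can run on, the continuation itself discloses the allocation.
2. **Control data.** Participants are their own controls, but under the H2O-only text no NBM session is scanned after 120 minutes.
3. **The feasibility aims.** The study wants to learn how long each protocol takes and whether full data can be collected under each. Neither can be judged while the number of scans in a full session is undecided.

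The late period also matters to the research question. If the first drink directly follows the baseline scan (an assumption), the second is at 60 minutes. A two-hour window counted from that drink then ends at 180 minutes, inside the disputed extension.

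**Working it through.** **The two rules side by side**

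| | Text within Protocol H2O | Later bullet |
|---|---|---|
| Force | optional | required |
| Protocols covered | H2O only | no restriction |
| Trigger | starting volume not regained | baseline not regained at two hours |
| Maximum extension | two hours | two hours |

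The trigger and the maximum agree. The force and the coverage do not. The NBM description, which stops at two hours, fits the first rule and not the second.

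**Scan counts** (30-minute schedule and 15 participants, both from the Protocol)

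- Scans every session has: 0, 30, 60, 90 and 120 min = 5.
- Possible extension: 150, 180, 210 and 240 min = 4, so at most 5 + 4 = 9.
- H2O-only rule: at most 15 × 4 = 60 late H2O scans and 0 late NBM scans.
- Later bullet: at most 60 late scans in each protocol, taken only in sessions not back to baseline.
- Session length if baseline is not regained: two hours or up to four, depending on the rule and, under the first rule, on whether the option is used.

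**Which scans are unblinded under the H2O-only rule**

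- The extended session at 0–120 min: no. These scans are finished before any extension starts.
- The extended session at 150–240 min: yes. Only H2O sessions reach these times.
- The participant's other (NBM) session: only if it comes second and the same sonographer does it. If NBM came first, its scans are already taken.

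**Selection in the late scans under either rule**

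A session is scanned at 150 min only if its 120-min reading was above its baseline reading, at 180 min only if the 150-min reading was also above, and so on. As an illustration, suppose every stomach is truly back at baseline and readings differ only by independent, identical normal error. To be scanned at 150, 180, 210 or 240 min, the baseline reading must be the lowest of 2, 3, 4 or 5 readings. The chance that it is the lowest of k readings is 1/k. The next reading is independent of that selection, so the mean apparent change equals minus the expected minimum of k standard normal readings.

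| Scan time (min) | k | Share still scanned, 1/k | Mean apparent change (reading SDs) |
|---|---|---|---|
| 150 | 2 | 0.50 | +0.56 |
| 180 | 3 | 0.33 | +0.85 |
| 210 | 4 | 0.25 | +1.03 |
| 240 | 5 | 0.20 | +1.16 |

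The true change is zero throughout. The table shows why late means should not be read as typical volumes. It does not measure the harm done by the contradiction, because any single rule that continues conditionally would select in the same way.

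**The case against.** The case against is substantial, and much of it limits the point.

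- **The later bullet may be the governing one.** It sits among bullets common to both protocols. If it governs, NBM sessions are extended on the same trigger, a late scan does not by itself reveal allocation, and late NBM scans can exist. This stands: the unblinding and the missing controls belong to the H2O-only reading. But nothing at hand says that reading is wrong, and the NBM description agrees with it.
- **A reader might infer that the later bullet extends everyone.** It does not. It applies only to sessions not back to baseline.
- **A reader might infer that blinding is lost for the whole of the slow-emptying sessions.** It is not. The extension begins after the 0–120 min scans, and the other session is exposed only under the conditions set out above. The Protocol does not say that one sonographer scans both days. The images may also hint at allocation after a 150 ml drink, whatever the rule.
- **A reader might infer that the sonographer must calculate volumes live, or that the operator chooses who is followed.** The Protocol does not say who compares a reading with baseline or who exercises the option. Blinding is to the protocol allocated, not to measured volume.
- **No analysis of mean volumes at 150–240 min is stated, and analysis detail may sit in an SAP.** This is correct, so the selection table is a caution and not an error in a stated analysis. It remains relevant because the Protocol bases planning SDs on volumes at specific intervals without limiting those intervals to the first two hours.

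**Conclusion.** The contradiction is real on two counts: optional against required, and H2O only against either protocol. Followed as written, the H2O-only text defeats the stated sonographer blinding for up to 4 late scans in each extended session, and for a later NBM session if the same sonographer does it. It also leaves up to 60 late H2O scans with no NBM counterpart. These are ceilings. The Protocol gives no basis for predicting how many sessions will be extended.

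A reader might go further and conclude that the main comparison is compromised. The documents do not support that. Every session in both protocols has the five scans from 0 to 120 min under either rule, and the only route by which those scans could be unblinded is the later NBM session just described. The selection figures rest on independent normal errors, no true change and no tolerance around baseline, and they apply equally to a reconciled conditional rule.

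In a 15-volunteer feasibility study with the common two-hour data in place, this is a should-fix. It is best settled before the first session because it directs conduct on the day. The later bullet's ending looks cut short in the text at hand; that may come from reading the PDF and is not counted here.

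**What to change.** 1. Reconcile the passages to one continuation rule worded identically for Protocol NBM and Protocol H2O, or to no continuation in either. Which of these is for the investigators to decide. Remove the wording that makes continuation optional, and bring the NBM description into line.
2. State that the H2O–NBM volume comparison, and the SDs carried into the future sample size, use the 0–120 min scans that every session has.
3. State that scans after 120 min, if kept, serve only to describe time to return to baseline, and are not summarised as mean volumes between protocols.

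If continuation is kept in both protocols, H2O sessions may still be extended more often, so a late scan could remain a hint to allocation, but it would no longer be proof. Dropping continuation removes the cue entirely, at the price of no information after 120 min.

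The cost is a change of protocol wording and, if continuation is kept, some NBM sessions lasting up to four hours instead of two.
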